## 8. STUDY CALENDAR

	Screening	Treatment									End of Treatment and Follow Up		
Visit Name	Screening	C1D1 Week 0 o	C1D14 Week 2	C2D1 Week 4 i	C2D14 Week 6	C3D1 Week 8	C5D1 Week 16	C8D1 Week 28	C11D1 Week 40	C13D28 Week 52	EOT Visit m	28 Day Safety FU Visit	6 Month FU Visit h
Visit Window	-14 days	Within 3 days of enrolment	+/- 2 days	+/- 4 days	+/- 4 days	+/- 7 days	+/- 7 days	+/- 7 days	+/- 7 days	+/- 7 days	+/- 7 days	+/- 7 days	+/- 28 days
Informed consent***	X												
Inclusion/Exclusion Criteria	X												
Demographics	X												
Prior GvHD Medication & Medical History	X												
Tuberculosis Skin Test / Interferon -gamma release assay f	X												
Ruxolitinib Dispensing k		X	X	X	X	X	X	X	X	X k			
Belumosudil Dispensing l				X i	X	X	X	X	X	X l	Taper & Discontinue		
Physical Examination a & ECOG performance status assessment	X	X	X	X	X	X	X	X	X	X	X	X	
Vital Signs b	X	X	X	X	X	X	X	X	X	X	X	X	
P-ROM assessment	X	X	X	X	X	X	X	X	X	X	X	X	
12 Lead ECG c	X												
Pregnancy Test d	X	X											
Hematology e	X	X	X	X	X	X	X	X	X	X	X	X	
Serum Chemistry f	X	X	X	X	X	X	X	X	X	X	X	X	
Virology j	X												
Pulmonary Function Test		X					X	X	X	X	X		
Modified Lee Symptom Scale		X		X		X	X	X	X	X	X		
NIH consensus based GvHD organ specific		X	X	X			X	X	X	X	X		

score and global severity score q													
IP return and accountability			X	X	X	X	X	X	X	X	X l		
Survival Status												X	X
Adverse Events l		Continuous											
Concomitant medications review	X	Continuous											X n
Correlative Samples (optional sub-study) q	X							X			X		

\*\*\*Consent should be done prior to any study specific screening assessment, according to the site ethics board approved process and site institutional timelines. Site should follow their site guidelines for consenting window (timeframe for prior to screening and prior to enrollment). Patient enrollment with Ozmosis@UHN is required. Please refer to section "Patient Enrollment".

- Complete physical examinations will be done at Screening and on C1D1 (i.e. weight, height, HEENT, Cardiovascular, Dermatological, Musculoskeletal, Respiratory, GI, Genitourinary, Neurological, Endocrine Metabolic, Blood Lymphatic, Other). Symptom directed physical exams will be performed for all subsequent visits as per study calendar. See Appendix A for ECOG Performance Status Scale
- Vital signs: Pulse rate, blood pressure, temperature and respiratory rate will be measured. Vitals will be measured prior to dosing.
- 12-lead ECG will be performed as per the timepoints in the study calendar and more frequently as indicated clinically (i.e. in the event of cardiovascular AEs, patient is hypokalemic, etc.).
- A negative **urine** pregnancy test is required for female patients at the time of screening. A negative **serum** pregnancy test is required for female patients of childbearing potential on C1D1 prior to treatment.
- Hematology will include: hemoglobin, hematocrit, RBC count, platelet count, absolute neutrophil count and differential WBC count.
- Serum chemistry will include: total proteins, albumin, calcium, phosphorous, total cholesterol, random plasma glucose, uric acid, BUN/urea, GFR, creatinine, total bilirubin, ALP, sodium, potassium, magnesium, serum bicarbonate, chloride, AST, ALT, LDH. These electrolytes and creatinine levels are to be checked more frequently as indicated clinically.
- Peripheral blood samples for correlative studies will be collected for plasma and mononuclear cells isolation at the timepoints indicated. Patient must have provided consent to participate in this optional sub-study. See the study lab manual for additional sampling details.
- Visit may be conducted remotely over the phone if preferred.
- In the event that at the intended C2D1 visit assessment the participant is experiencing Grade  $\geq 3$  AE(s), treatment with belumosudil should not begin. This visit will be considered an unscheduled visit and the C2D1 visit should be rescheduled. The participant can continue on ruxolitinib alone and should be followed for resolution of the Grade  $\geq 3$  AE(s). If the Grade  $\geq 3$  AE(s) improve to Grade  $\leq 2$  or resolve completely within 4 weeks, the participant will still be eligible to receive belumosudil. In this case, they should come back in for a true C2D1 visit and can complete all the necessary assessments as well as belumosudil dosing. If the Grade  $\geq 3$  AE(s) does not recover within 4 weeks, the participant will move on to the End of Treatment visit and discontinue study. If there are any questions or concerns about the patient status and treatment in these scenarios, this should be discussed with the sponsor.
- HIV, HBsAg, HBV DNA, HCV antibody, and HCV RNA.
- Ruxolitinib may continue on past the C13D28 visit as per standard of care and if, in the opinion of the treating investigator, the patient is receiving clinical benefit. Tapering of ruxolitinib should be done slowly as per the product monograph with documented CR or PR, starting with a 50% dose reduction every 2 months (56 days). Initial dose reduction is to 5 mg orally BID. If sustained cGvHD response is observed (i.e. no worsening of cGvHD signs and symptoms), patient is further tapered by a second 50% dosage reduction to 5 mg orally QD for an additional 2 months (56 days), prior to cessation.
- Patients whose cGVHD has not progressed at the time of study treatment completion or discontinuation of combination treatment of belumosudil and ruxolitinib for reasons other than AEs should be tapered off belumosudil by reducing the dose every 2 weeks (14 days) as described below:  
Starting dose of 200mg BID  $\rightarrow$  200mg QD  $\rightarrow$  200mg QOD  $\rightarrow$  Discontinue **OR** Starting dose of 200mg QD  $\rightarrow$  200mg QOD  $\rightarrow$  Discontinue
- For those participants who completed all treatment visits, the C13D28 visit can be considered the End of Treatment Visit.
- Only subsequent therapies used to treat cGvHD need to be captured during the period from the 28-day safety follow up and the 6 month follow up visit
- The protocol treatment is to begin within 3 working days of patient enrollment. Any screening assessments performed within 24 hours of C1D1 can be used to fulfill C1D1 requirements and do not need to be repeated.
- Only subsequent cGvHD treatments will be captured during follow up, while other conmeds requiring for supportive or palliative treatment will not be captured (e.g. Tylenol, nasal spray, etc.)
- See Tables 2 and 3, as well as Appendix C

r. Prior to initiating ruxolitinib (Cycle 1 Day 1), a tuberculosis skin test or interferon-gamma release assay should be performed in accordance with the approved JAKAVI® (ruxolitinib) product monograph to screen for latent tuberculosis infection, with results interpreted cautiously in immunocompromised patients. Positive results should prompt appropriate evaluation and management per institutional guidelines before starting isoniazid therapy. If the patient had been already treated with isoniazid prophylaxis for 6 months due to prior history of tuberculosis skin test or interferon-gamma release assay, this test will be exempted

---

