## SYNOPSIS

Study Title:	A Phase 2 study of Belumosudil combined with Ruxolitinib (BELRUX) as 2nd line therapy to treat chronic Graft versus Host Disease (cGvHD) after steroid failure
Primary Objectives and Endpoints:	
To evaluate the efficacy, tolerability and safety of combination treatment of belumosudil with ruxolitinib as a second line therapy for steroid refractory cGvHD
 
 
1) Efficacy will be assessed using overall response rate (ORR) as per the NIH cGvHD Consensus Response Criteria at 24 weeks of combination treatment (C8D1) of belumosudil with ruxolitinib (i.e., 28 weeks after C1D1).
 
2) Tolerability and safety will be assessed by the incidence and severity of adverse events (AEs) throughout the treatment duration using CTCAE v5.0 grading.
 

Secondary Objectives and Endpoints:	
To evaluate the response achievement with combination treatment of belumosudil with ruxolitinib as second line treatment for cGvHD.
 
 
1) ORR as per the NIH cGvHD Consensus Response Criteria after 48 weeks of combination treatment of belumosudil with ruxolitinib (i.e., 52 weeks after C1D1).
 
2) Failure-free survival (FFS) after 24 and 48 weeks of combination treatment of belumosudil with ruxolitinib (i.e., 28 and 52 weeks after C1D1). FFS is defined as the time from treatment initiation until the occurrence of treatment failure.
 
3) Durable response rate in patients who achieve complete or partial response with combination treatment of belumosudil with ruxolitinib as assessed at 52 weeks from C1D1. Durable response is defined as sustained improvement in symptoms or absence of disease progression from the time of treatment initiation.
 
4) Overall GvHD symptom burden improvement, serially measured using the modified Lee Symptom Scale (see Appendix D).
 

Exploratory Objectives and Endpoints:	
To evaluate improvement in musculoskeletal involvement of sclerotic GvHD using the P-ROM score measurement.
 
 
1) Changes in the P-ROM score after 12, 24, and 48 weeks of combination therapy for patients who have developed sclerotic GvHD in musculoskeletal involvement of GvHD
 

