	
End of Treatment Visit
 
 
• Physical Examination & ECOG
 
• Vital Signs
 
• Hematology
 
• Serum Chemistry
 
• AE Assessment
 
• Concomitant Medications
 
• NIH consensus based GvHD organ specific score and global severity score (i.e. mild vs moderate vs severe grade)
 
• Modified Lee Symptom Scale
 
• P-ROM (Photographic Range-Of-Motion) assessment
 
• Pulmonary Function Test
 
• IP return and accountability
 
• Correlative Samples
 
 
Follow-up Visit
 
 
• Survival status
 
• Concomitant Medications (new cGvHD therapies only)
 

Response:	
- Overall response rate (ORR) will be evaluated at 24 and 48 weeks after initiation of combination therapy
 
- Failure-free survival (FFS) will be evaluated using Kaplan-Meier method. The FFS rate will be evaluated at 24 and 48 weeks after initiation of combination therapy
 
- Durable response after response achievement will be evaluated only in the patients who achieved CR or PR during the treatment period (any response)

Safety Variables & Analysis:	
The safety and tolerability of study treatment will be evaluated by means of AE reports, physical examinations, and laboratory safety evaluations. Terminology Criteria for Adverse Events (CTCAE) V5.0 will be used for grading of AEs.
 
Interim safety data will be examined on an ongoing basis to ensure patient safety.

Statistical Analysis:	
Statistical Analysis: This is a single-arm phase II study with a sample size of 63 patients (accounting for 10% dropout) to provide 90% power to detect an improvement in ORR from 49.7% (null) to 66% (alternative) at 6 months using a two-sided exact test at <math>\alpha=0.10</math>
 
Populations:
 
 
- Intent-to-Treat (ITT): All enrolled patients.
 
- Safety: All patients receiving <math>\geq 1</math> dose of belumosudil.
 
- Efficacy: All patients completing <math>\geq 1</math> cycle of belumosudil with baseline assessment.
 

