### **2.1 Estimated Study Duration**

The enrollment period of the study is expected to be approximately 12-18 months. The screening period may last up to 14 days. The treatment period for an individual patient is expected to be approximately 52 weeks from the date of starting therapy (i.e., Cycle 1 Day 1). Patients will be followed for evidence of progression of cGVHD, survival, and unexpected toxicity (if any) for 24 weeks after the end of treatment visit.

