**Figure 1. Participant treatment schema**

## 3. OBJECTIVES

Primary Objectives	Primary Endpoints
To evaluate efficacy, tolerability and safety of combination treatment of belumosudil with ruxolitinib as second line therapy for steroid-refractory cGvHD.	
 
Efficacy will be assessed using overall response rate (ORR) as per the NIH cGvHD Consensus Response Criteria at 24 weeks of combination treatment (C8D1) of belumosudil with ruxolitinib (i.e., 28 weeks after C1D1).
 
Tolerability and safety will be assessed by the incidence and severity of adverse events (AEs) throughout the treatment duration using CTCAE v5.0 grading.
 

Secondary Objectives	Secondary Endpoints
To evaluate the response achievement with combination treatment of belumosudil with ruxolitinib as second line treatment for cGvHD.	
 
ORR as per the NIH cGvHD Consensus Response Criteria after 48 weeks of combination treatment of belumosudil with ruxolitinib (i.e., 52 weeks after C1D1).
 
Failure-free survival (FFS) after 24 and 48 weeks of combination treatment of belumosudil with ruxolitinib (i.e., 28 and 52 weeks after C1D1). FFS is defined as the time from treatment initiation until the occurrence of treatment failure.
 
Durable response rate in patients who achieve complete or partial response with combination treatment of belumosudil with ruxolitinib as assessed at 52 weeks from
 

	
C1D1. Durable response is defined as sustained improvement in symptoms or absence of disease progression from the time of treatment initiation.
 
4. Overall GvHD symptom burden improvement, serially measured with a modified Lee Symptom Scale (see Appendix D).

Exploratory Objectives	Exploratory Endpoints
To evaluate improvement in musculoskeletal involvement of sclerotic GvHD using the P-ROM score measurement.	1. Changes in the P-ROM score after 12, 24, and 48 weeks of combination therapy in patients who have developed sclerotic GvHD in musculoskeletal involvement of GvHD

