## 10.9 Exceptions and Non-Reportable SAEs

**Progressive disease**, death due to progressive disease, and relapse of primary malignancy, will not be reportable as an SAE in this study. Relapse of the underlying malignancy is not reported as an adverse event if it is clearly consistent with the suspected relapse. Clinical symptoms of relapse may be reported as an AE if the symptom cannot be determined as exclusively due to the relapse of the underlying malignancy or does not fit the expected pattern of relapse for the disease under study. If there is any uncertainty of an AE being due only to cancer it should be reported as an AE or SAE.

**Elective procedures** requiring hospitalization will not be considered SAE's if they were pre-planned prior to signing consent; however, other events may occur during this hospitalization that may be considered serious or non-serious adverse events and will need to be captured according to the protocol SAE reporting period if hospitalization is prolonged.

---

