## 11.3 Evaluation of Study Endpoints

### 11.3.1 Evaluation of the Primary and Secondary Endpoints

Overall response rate (ORR) will be evaluated at 24 and 48 weeks after combination therapy (i.e. 28 and 52 weeks after enrollment), respectively. The proportion of responders and its 95% confidence interval (using exact binomial methods) will be calculated.

Failure-free survival (FFS) will be evaluated using Kaplan-Meier method. The FFS rate will be evaluated at 24 and 48 weeks after combination therapy (i.e. 28 and 52 weeks after enrollment), The composite endpoint of failure is defined as 1) GvHD progression or loss of response requiring switch of systemic GvHD treatment, 2) relapse of primary hematologic disease and 3) non-relapse mortality.

Durable response after response achievement will be evaluated only in the patients achieved CR or PR (any response). The Kaplan-Meier estimate will be calculated from the date of CR/PR achievement to the date of losing response/progression or death from any cause.

GvHD symptom burden improvement, measured serially by the modified Lee Symptom Scale, will be evaluated using repeated measure based on the general linear model. If p-value is less than 0.05, it demonstrates statistically significant change over time within subject.

The Modified Lee symptom score (mLSS) will be used to reflect a symptom burden in cGvHD study patients. The symptoms will be assessed serially and will be evaluated using repeated measure based on the general linear model. If p-value is less than 0.05, it demonstrates statistically significant change over time within subject. The score assesses 7 different organs/areas including skin, eye/mouth, breathing, eating/digestion, muscle/joints, energy, and mental/emotional health. The sum of these domains will be calculated to derive the total mLSS. Clinically meaningful improvement in mLSS is defined as a reduction of  $\geq 7$  points in overall mLSS. Longitudinal change in mLSS is analyzed by repeated measures using generalized linear model over time, evaluating within-subject and between-subject effects. In addition, the proportion of the patients showing clinically meaningful improvement in mLSS is analyzed longitudinally at 12, 24, and 48 weeks. In addition, the best improvement in mLSS is also calculated in each subject and plotted.

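### Post-treatment contact is timed from end of treatment rather than from C1D1 and has no item for relapse, so some 52-week FFS outcomes cannot be observed

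*Protocol*

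**What the plan says.** - **Landmarks.** Protocol Section 3 lists "Failure-free survival (FFS) after 24 and 48 weeks of combination treatment of belumosudil with ruxolitinib (i.e., 28 and 52 weeks after C1D1"). The synopsis sets the origin: "FFS is defined as the time from treatment initiation until the occurrence of treatment failure". Section 11.3.1 repeats the two landmarks and specifies Kaplan-Meier.
- **Failure events.** Section 11.3.1 counts cGvHD progression or loss of response that requires a change of systemic treatment, then "2) relapse of primary hematologic disease and 3) non-relapse mortality". Section 2 words the composite differently: progression or flare counts with or without ruxolitinib tapering, and no change of therapy is required.
- **Promised follow-up.** Section 2.1, and the synopsis in the same terms: "Patients will be followed for evidence of progression of cGVHD, survival, and unexpected toxicity (if any) for 24 weeks after the end of treatment visit".
- **Scheduled follow-up.** The study calendar (Section 8) has two contacts after EOT. The 28-day safety visit includes examination, ECOG, vital signs, P-ROM, hematology, chemistry and survival status. The column "6 Month FU Visit" (±28 days, may be by phone) marks survival status and concomitant medication only. The synopsis limits the latter to "Concomitant Medications (new cGvHD therapies only").
- **Other routes.** Section 9 counts a new systemic cGvHD therapy as treatment failure and captures such therapies through the 24-week follow-up. Section 10.9 states that progressive disease, death due to it, and "relapse of primary malignancy, will not be reportable as an SAE in this study".

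**The concern.** The endpoint clock starts at C1D1 and the follow-up clock starts at EOT. They agree only for patients who stay on treatment to about week 28 or beyond. Stopping for intolerance, non-compliance or preference is not a failure under Section 11.3.1, so a patient who stops early for such a reason stays at risk but is no longer contacted at week 52. Kaplan-Meier then treats that patient as failing at the rate of those still observed. If early stoppers do worse, 52-week FFS is overstated.

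The second gap concerns content and affects anyone who stops before week 52, including those who stop after week 28. A non-fatal relapse after EOT is an FFS event with no form item and no SAE route. Progression that does not lead to a new drug, a failure under the Section 2 wording, has no item at the last contact. An analysis plan cannot recover events that were never recorded.

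**Working it through.** **1. Landmarks.** The lead-in is 4 weeks of ruxolitinib alone: 4 + 24 = 28 and 4 + 48 = 52 weeks. The protocol's figures reproduce.

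**2. Last contact for a patient stopping at week t.** Nominally t + 24; with the ±28-day window, t + 20 to t + 28. Week 52 is covered when t ≥ 52 − 24 = 28, or from t ≥ 24 (visit at the late edge) to t ≥ 32 (visit at the early edge).

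| Stop week | Last contact (window) | Nominal gap to week 52 |
|---|---|---|
| 8 | 32 (28–36) | 20 weeks |
| 16 | 40 (36–44) | 12 weeks |
| 24 | 48 (44–52) | 4 weeks |
| 28 | 52 (48–56) | 0 |

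The week-28 landmark is nominally covered for any stop at week 4 or later. Week 8 is a route the protocol itself creates: under Section 5.1, a Grade ≥3 AE at the intended C2D1 (week 4) that does not recover within 4 weeks leads to EOT.

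**3. What is captured after EOT, by FFS component.**
- Progression or loss of response requiring a switch: yes, through new cGvHD therapies, for 24 weeks.
- Death: yes, through survival status. No follow-up item asks for its cause.
- Non-fatal relapse: no item.
- Progression or flare without a switch (Section 2 wording): the 28-day visit gives partial information, since P-ROM and liver tests are Table 7 criteria. There is no item at the 6-month contact.

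**4. Size of the censoring bias.** The protocol gives no FFS assumption and no stop-time distribution, so the following are assumed: 63 patients; m = 6 (close to the 10% dropout in Section 11.1) or 9 who stop failure-free at week t; 60% FFS at week 52 in the rest; exponential failure; hazard multiplied by k after stopping; censoring at t + 24.

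- h = −ln(0.60)/52 = 0.00982 per week.
- True FFS(52) = [(63 − m) × 0.60 + m × exp(−k·h·(52 − t))]/63.
- The Kaplan-Meier value in expectation is exp(−∫ pooled hazard), integrated from 0 to 52. The pooled hazard at week u is the average over A(u) = (63 − m)·exp(−h·u) continuing patients with hazard h and B(u) stoppers. B(u) = m with hazard 0 up to t, then m·exp(−k·h·(u − t)) with hazard k·h. Stoppers leave the risk set at t + 24.
- Example, m = 6, t = 8, k = 2: truth = (34.2 + 6 × 0.421)/63 = 58.3%; Kaplan-Meier 59.2%; difference 0.9 points.

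Overstatement in percentage points:

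| m | t | k = 2 | k = 3 | k = 5 |
|---|---|---|---|---|
| 6 | 8 | 0.9 | 1.2 | 1.3 |
| 6 | 16 | 0.6 | 0.9 | 1.0 |
| 6 | 24 | 0.2 | 0.3 | 0.4 |
| 9 | 8 | 1.3 | 1.9 | 2.0 |
| 9 | 16 | 0.9 | 1.3 | 1.5 |
| 9 | 24 | 0.3 | 0.5 | 0.6 |

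With k = 1 the difference is zero, as it should be. The range is 0.2–1.3 points for 6 stoppers and 0.3–2.0 for 9.

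**5. Missed relapses.** Each patient counted as failure-free at week 52 despite an unrecorded relapse adds up to 1/63 = 1.6 points.

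**The case against.** Several points on the other side stand.

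- A reader might infer that 52-week FFS is unknown for everyone who stops before week 28. It is not. Patients who stop for progression with a switch, relapse or death already have their event. Section 5.6 also treats Lack of Response or Mixed response as progression for analysis. Only those who stop failure-free and remain so to last contact have a gap.
- A reader might infer that later progression is never captured. Progression as Section 11.3.1 defines it shows up as a new systemic therapy, collected for 24 weeks, and the 28-day visit is more than a survival check.
- A reader might reach a larger bias by setting 60% against 57 × 0.60/63 = 54.3%, and conclude 5 to 7 points for FFS of 50–70%. That ignores the 24 weeks in which early stoppers are still observed. It is not a true bound either: if all six reached last contact failure-free and then all failed before week 52, the overstatement would be about 8 to 9 points. That pattern is extreme.
- Early stoppers have not necessarily lost both drugs. Ruxolitinib is standard of care from the local pharmacy, so a much higher hazard after stopping is not established.
- Exemption from SAE reporting does not prevent eCRF recording, and relapse on treatment is documented as a discontinuation reason.
- FFS carries no success threshold. At 60% with 63 patients the 95% half-width is about 1.96 × √(0.6 × 0.4/63) = 12 points, well above the bias computed here.

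These limit the size of the problem. They do not supply a week-52 contact or a relapse item, or remove the mismatch between Section 2.1 and the calendar.

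**Conclusion.** The point holds in limited form. Patients who stop failure-free before about week 28 (24 to 32 with the window) have no scheduled contact at the 52-week landmark. Non-fatal relapse after EOT has no collection item. The progression follow-up stated in Section 2.1 and the synopsis has no matching item at the last contact. The direction of bias is probably upward and its size modest: about 0.2 to 2 points under the assumed stop times, 60% FFS and 2- to 5-fold hazard, plus any missed relapses. The number of early stoppers is not given by the protocol, and reading the 10% dropout as failure-free stops before week 28 is itself an assumption. Severity is minor to moderate: FFS is secondary, and the success rule in Section 11.1 rests on response at 6 months. The change is still worth making, because uncollected events cannot be repaired at analysis.

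**What to change.** - In the calendar, Section 2 and the synopsis, hold the existing remote contact at the later of 24 weeks after EOT and 52 weeks after C1D1. Patients who stop at week 28 or later keep the present timing.
- Add to that contact: relapse of the primary disease with date; cGvHD progression or flare with date; start date of and reason for any new systemic cGvHD therapy; date and cause of death.
- Reconcile Section 2.1 and the synopsis duration text with what the calendar collects. A dated progression item serves either wording of the failure definition (Section 2 or Section 11.3.1); those two should also be reconciled.

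The cost is an amendment to one calendar column and the matching text, one eCRF page, and somewhat longer follow-up for a few early stoppers. No visit is added, since the contact may already be by phone. The change should be in place before early stoppers pass their present last contact.

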Study Design:	This is a phase II, non-randomized, open-label study in patients with moderate to severe cGvHD who have failed to respond or are intolerant of first-line steroid therapy. Patients will receive combination therapy with two oral agents (belumosudil, ruxolitinib) with documented individual efficacy as second line treatment in cGvHD patients.

	Participants will begin on 10 mg BID of oral ruxolitinib monotherapy for one cycle (i.e. Cycle 1). Each cycle is equal to 28 days. Upon the initiation of Cycle 2, patients will begin taking belumosudil in addition to ruxolitinib, at a dose of 200 mg OD or 200 mg BID (if on a PPI). Patients will remain on combination therapy for 48 weeks (i.e. 12 cycles), until progression of cGVHD, or intolerance to either agent, whichever occurs sooner. A visit will be conducted at the end of treatment, 28 days post-end of treatment as well as 24 weeks (6 months) post-end of treatment.
Duration:	The enrollment period of the study is expected to take 12-18 months. The screening period for each patient may last up to 14 days. The treatment period for an individual patient is expected to be approximately 52 weeks from the date of starting therapy (Cycle 1 Day 1). Patients will be followed for evidence of progression of cGVHD, survival, and unexpected toxicity (if any) for 24 weeks after the end of treatment visit.
Planned Total Sample Size:	A maximum of 63 patients will be enrolled.
Investigational Product Administration:	Belumosudil will be administered as an oral dose of 200 mg OD or 200 mg BID (if patient is on a proton pump inhibitor (PPI))

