--	--

	
13. Patients with known active CNS disease (malignant involvement of CNS).
 
14. Patients with active acute GvHD grade III-IV.
 
15. History or other evidence of severe illness or any other conditions that would make the patient, in the opinion of the treating Investigator, unsuitable for the study (such as malabsorption syndromes, poorly controlled psychiatric disease or coronary artery disease).
 
16. Known hypersensitivity to belumosudil, ruxolitinib or any of their excipients
 
17. Patients unable to swallow oral medications
 
18. Female participants who are pregnant or breastfeeding

Patient Screening Assessments:	
 
• Written Informed Consent
 
• Inclusion/Exclusion Criteria
 
• Demographics
 
• Medical History & Prior GvHD Treatments
 
• Physical Examination (includes height and weight) & ECOG performance status assessment
 
• Vital Signs
 
• 12-lead ECG
 
• Urine pregnancy test in biologically female patients
 
• Hematology
 
• Serum Chemistry
 
• Virology
 
• Concomitant Medications
 
• Correlative Sampling (optional)
 
• P-ROM (Photographic Range-Of-Motion) assessment
 

Treatment and Post-Treatment Assessments:	
Assessments to be completed on visits as per the Study Calendar
 
Treatment Phase (0, 2, 4, 6, 8, 16, 28, 40, 52 weeks)
 
 
• Physical Examination & ECOG performance status assessment
 
• Vital Signs
 
• Hematology
 
• Serum Chemistry
 
• AE Assessment if required
 
• Ruxolitinib and belumosudil administration
 
• Concomitant Medications
 
• NIH consensus based GvHD organ specific score and global severity score (i.e. mild vs moderate vs severe grade)
 
• NIH consensus based GvHD response assessment
 
• Modified Lee Symptom Scale
 
• P-ROM (Photographic Range-Of-Motion) assessment
 
• Serum pregnancy test in biologically female patients
 
• Pulmonary Function Test
 
• IP return and accountability
 
• Correlative Samples (as per the Study Calendar, optional)
 

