## 5. STUDY TREATMENT

### 5.1 Study Drug Administration

The Investigational Medicinal Product (IMP), Belmosudil, will be provided by Sanofi as 200 mg tablets.

Ruxolitinib will be dispensed as either 5 or 10 mg tablets, and will be obtained through the site's local pharmacy, as it will be administered per SOC.

All patients will receive open-label IMP. Responsibility for treatment of patients rests with the QI. Prior to initiating ruxolitinib (Cycle 1 Day 1), a tuberculosis skin test or interferon-gamma release assay should be performed in accordance with the approved JAKAVI® (ruxolitinib) product monograph to screen for latent tuberculosis infection, with results interpreted cautiously in immunocompromised patients. Positive results should prompt appropriate evaluation and management per institutional guidelines before starting isoniazid therapy. If the patient had been already treated with isoniazid prophylaxis for 6 months due to prior history of tuberculosis skin test or interferon-gamma release assay, this test will be exempted.

Eligible participants in this study will be started on ruxolitinib monotherapy orally at the standard recommended dose of 10 mg BID for 4 weeks (28 days). After one full cycle of ruxolitinib treatment (i.e., C2D1), the participant will have an AE assessment and, unless Grade  $\geq 3$  AE is observed, will continue on the same dose of ruxolitinib **plus** oral belumosudil 200 mg QD (or BID if receiving concomitant PPI) starting on C2D1.

In the event that the participant is experiencing Grade  $\geq 3$  AE(s) at the intended C2D1 visit assessment, treatment with belumosudil should not begin. This visit will be considered an unscheduled visit and the C2

D1 visit should be rescheduled. The participant can continue on ruxolitinib alone and should be followed for resolution of the Grade  $\geq 3$  AE(s). If the Grade  $\geq 3$  AE(s) improves to Grade  $\leq 2$  or resolves completely within 4 weeks, the participant will still be eligible to receive belumosudil. In this case, they should come back in for a true C2D1 visit and can complete all the necessary assessments as well as belumosudil dosing. If the Grade  $\geq 3$  AE(s) does not recover within 4 weeks, the participant will complete the End of Treatment visit and discontinue study. If there are any questions or concerns about the patient status and treatment in these scenarios, this should be discussed with the sponsor.

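### No pregnancy test is scheduled at C2D1, when belumosudil is first given; the last scheduled test is 28 days earlier

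*Protocol*

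**What the plan says.** Three places in the protocol set the testing schedule, and they agree.

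- Section 8 (Study Calendar): the row "Pregnancy Test" is marked at Screening and C1D1 and at no later visit.
- Section 8, footnote d: urine at screening, and for the second test a negative serum "pregnancy test is required for female patients of childbearing potential on C1D1 prior to treatment".
- Section 9.3: the same two tests, with exclusion if either is positive.

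Section 5.1 starts ruxolitinib alone at C1D1 for 28 days, then adds "oral belumosudil 200 mg QD (or BID if receiving concomitant PPI) starting on C2D1". That start depends on an adverse event assessment. A Grade 3 or higher event postpones it, and belumosudil may still begin if the event improves within four weeks. The C2D1 visit is then held again with its assessments.

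The synopsis names a further item, "Serum pregnancy test in biologically female patients", under the heading "Treatment Phase (0, 2, 4, 6, 8, 16, 28, 40, 52 weeks"). The same block is introduced by "Assessments to be completed on visits as per the Study Calendar".

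Pregnancy is an exclusion (Section 4.2, item 18) and ends treatment without exception (Section 5.6).

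**The concern.** The protocol treats pregnancy as an absolute bar, and it has one visit at which the decision to start the investigational drug is taken. That decision looks at adverse events and not at pregnancy. A site that follows the plan exactly could give the first belumosudil dose to a woman who conceived during the ruxolitinib lead-in and does not yet suspect it.

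What is at stake is an avoidable fetal exposure to a second drug. Power, the type I error rate and the response endpoint are not affected.

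**Working it through.** The protocol gives no figure of its own for this interval, so the check is date arithmetic plus a reading of the calendar.

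**Inputs**
- Last scheduled test: C1D1, Week 0 (Section 8, footnote d; Section 9.3).
- Cycle length: 28 days (Section 2).
- First belumosudil dose: C2D1, Week 4 (Section 5.1; dispensing row in Section 8).
- C2D1 visit window: plus or minus 4 days (Section 8).
- Longest hold for a Grade 3 or higher event: 4 weeks, or 28 days (Section 5.1).

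**Age of the last test at the first belumosudil dose**
- On schedule: 28 days.
- With the window: 28 − 4 = 24 to 28 + 4 = 32 days.
- With the full hold: 28 + 28 = 56 days.
- With the full hold and a late visit: 32 + 28 = 60 days.

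**Does the synopsis supply a C2D1 test?** Its heading lists nine treatment weeks (0, 2, 4, 6, 8, 16, 28, 40, 52), and Week 4 is C2D1. At those nine visits the calendar marks:

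| Item in the synopsis list | Visits marked in the calendar | Count |
|---|---|---|
| Pregnancy test | C1D1 | 1 of 9 |
| Pulmonary function test | C1D1, C5D1, C8D1, C11D1, C13D28 | 5 of 9 |

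The row "Pulmonary Function Test" shows that an item in the synopsis list need not be done at every listed week. The list takes its timing from the calendar, and the calendar leaves Week 4 blank. So the synopsis neither schedules a C2D1 test nor contradicts the calendar.

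**Does a rescheduled C2D1 supply one?** No. The repeated visit calls for the assessments of that visit, and the calendar has no pregnancy test among them.

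**How many women are concerned?** The protocol does not say. It states only "A maximum of 63 patients will be enrolled", and these are patients of both sexes. The number of women of childbearing potential is some part of 63, and no frequency of conception can be derived.

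**The case against.** The strongest reply is that the text contains no error. The calendar, its footnote and Section 9.3 are consistent, and the C1D1 test comes before the first study treatment, as it should. Women must use two contraceptive methods, be surgically sterile or abstain from enrolment onward (Section 9.3). They are told to report a suspected pregnancy at once (Section 10.11), and pregnancy stops treatment. Nothing forbids a test when there is a clinical reason. The protocol applies the same pregnancy rules to both drugs and shows no hazard peculiar to belumosudil. The argument for testing at C2D1 could also be made for every one of the 12 combination cycles.

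Much of this stands. The existing controls are substantial, the number at risk is unknown, and a C2D1 test covers only the lead-in. The protocol's own practice answers part of it, though. At C1D1 it does not rely on contraception, or on a screening urine test taken during a screening period of up to 14 days. It asks for a fresh negative result before the drug is started. C2D1 is the one later visit at which a new drug is started and at which the start is already conditional. That is a reason to choose C2D1 without deciding the question for later cycles.

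Three stronger readings are tempting, and none is supported:

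- *A reader might infer that no pregnancy test at all precedes belumosudil.* Two do, at screening and at C1D1. What is missing is one at C2D1.
- *A reader might infer that the synopsis contradicts the calendar.* It defers to the calendar.
- *A reader might infer that a C2D1 test would stop every such start.* A conception in the last days of the lead-in may not yet be detectable.

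**Conclusion.** The point holds as a modest safety improvement and not as an error or contradiction in the protocol. When belumosudil starts, the last scheduled pregnancy test is 28 days old. It is 24 to 32 days old within the visit window, and about 56 to 60 days old when the full adverse event hold is used. The longer figures apply only to patients held for a Grade 3 or higher event.

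A test at C2D1 can be expected to find most conceptions of the lead-in. That is a clinical assumption, because the documents give no detection figure. It would not reverse ruxolitinib exposure already incurred in Cycle 1, and it would not detect a conception during the following 48 weeks of combination treatment. The primary analysis is unaffected.

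**What to change.** 1. In the Section 8 calendar, mark the pregnancy test at C2D1.
2. Add to footnote d and to Section 9.3: *Female patients of childbearing potential must also have a negative pregnancy test before the first dose of belumosudil at C2D1, including a rescheduled C2D1. Serum from the blood drawn at that visit is used, or urine if no same-day serum result can be had.*
3. Align the synopsis line with the calendar: *Serum pregnancy test in female patients of childbearing potential at C1D1; serum or urine pregnancy test at C2D1 before the first belumosudil dose.* This also brings the synopsis, which now refers to all biologically female patients, into line with the population that footnote d names for the C1D1 test.

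Whether to test again in later cycles is a separate clinical decision for the sponsor.

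The cost is one calendar mark, one added requirement in two places, one synopsis line, and one assay per woman of childbearing potential. Hematology and serum chemistry are already drawn at C2D1, so no visit is added. The practical burden is that the result must be in hand before dosing, and the urine option addresses that.
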